Obesity and fat accumulation are often assessed using anthropometric measures such as body mass index z-score (BMIz) based on height and weight. Though useful to classify obesity status at a population level, we will use more precise and direct quantification of fat accumulation via MRI and DXA. Health consequences associated with obesity differ based on where adipose tissue is stored, for instance subcutaneously between the skin and muscle versus internally, such as within the chest, abdomen, and pelvis (i.e. visceral fat).29 Using the WAIST cohort, our research team observed that trunk fat, which is fat located centrally in the body excluding the extremities, affects adolescents' metabolic risk.¹⁸ Recent advances in body composition imaging allow for the examination of specific depots of fat in the pediatric population, providing sufficient precision to evaluate individual and group differences and to track changes in fat mass over time. Our research team previously identified through an extensive literature review that there are little data available on visceral fat in children and adolescents, and even less data measured in a longitudinal fashion over time.30 Through an examination of the cross-sectional data from the WAIST cohort, we identified ethnic and sex differences in visceral fat.₁₆ However, we do not know how the accumulation of trunk or visceral fat affects physical activity, sedentary behavior, or cardiometabolic risk factors. A systematic review of 32 studies indicated a relationship among children's fat gains with reduced physical activity and increased sedentary behavior, but stronger measurement methods and stratification by subgroup are needed.31 Therefore, the present project will provide important, timely data on the association between fat accumulation and children's activity levels using MRI and DXA technologies in a diverse sample of children and adolescents.

Activity Profiles and How Activity Varies by Obesity Status and Race

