BMIz- BMI percentile and BMIz will be calculated based on the participant's age, height, and weight using the CDC 2000 growth charts.⁶¹ Severe obesity will be categorized as $\geq 120\%$ of the 95th BMI percentile.¹⁵

Waist circumference - will be measured at the natural waist (halfway between inferior border of rib cage and superior aspect of iliac crest) with clothing moved out of the way.

Body composition

DXA- Total body fat and trunk fat will be assessed by whole-body DXA using a GE iDXA scanner (GE Medical Systems, Milwaukee, WI) to quantify total and regional body fat (including trunk fat).

DXA Instructions given to participant: This scan measures the amount of bone, muscle, and fat in your body. The scan will be performed using a whole-body scanner. You will be required to wear a hospital gown, to remove all metal-containing objects from your body, and to lie down on the table. You will be carefully positioned on the table, and your legs will be placed together using two Velcro straps. A scanner emitting low energy X-rays and a detector will pass along your body. You will be asked to remain completely still while the scan is in progress. The scan takes approximately ten minutes.

MRI - Visceral fat, i.e. visceral adipose tissue, will be assessed by water-fat shifting MRI using the General Electric Discovery 750w 3.0 Tesla (GE Medical Systems, Milwaukee, WI). IDEAL-IQ imaging technique will be used to generate water-only, fat-only, in-phase, and out-of-phase echoes in a single acquisition with a 20-second breath-hold. For female subjects ages 12 and above or females under the age of 12 who are menstruating as verbally confirmed by a parent or legal guardian, a negative urine pregnancy test will be required prior to DXA or MRI scans.

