A fasting sample of blood will be taken by a trained phlebotomist following standardized clinic procedures. The participant will be offered EMLA cream (lidocaine 2.5% and prilocaine 2.5%) to minimize pain related to blood draws. Serum concentrations of glucose, triglycerides, low density lipoprotein cholesterol (LDL-C), and high density lipoprotein cholesterol (HDL-C) will be obtained from a DXC600 manufactured by Beckman Coulter. Serum CRP levels are determined by immunoassay with chemiluminescent detection, run on an Immulite 2000 manufactured by Siemens. Insulin will be assayed on the Siemens Immulite 2000. Approximately two teaspoons of blood will be collected.

An aliquot of whole blood and aliquot of serum will be stored in case further tests are needed and if further consent is obtained from the subject.

Cardiometabolic risk factors

Resting blood pressure – will be assessed using standard clinical procedures on a standard sphygmomanometer.₆₂

Cardiometabolic risk factors - Elevated cardiometabolic risk (i.e. metabolic syndrome) will be categorized as the presence of three or more cardiometabolic risk factors using the established criteria in the 2011 National Institutes of Health Guidelines for Cardiovascular Health and Risk Reduction in Children and Adolescents.₆₃

24-hour Dietary Recall (ASA-24)

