Analyses to test Hypothesis 2 will be conducted using a series of linear regression models (i.e. linear mixed effects models). Based on difference score between Years 0 and 2 for total body fat, the group will be divided into two dichotomous groups using percentiles: high fat gainer (HFG) and low fat gainer (LFG). These variables will be used to predict changes in physical activity, sedentary behavior, and each cardiometabolic risk factor in linear mixed effect models. Covariates will include age, sex, dietary intake, and race. School term vs. school holiday will be considered as an additional covariate if time of year is significantly associated with the independent and dependent variables. Secondary analysis will use MRI and DXA as covariates in the model (namely the visceral, trunk, and total body fat). As previously reported, variable select criteria (including LASSO and support vector machine) will be used to determine which combination of these variables best explains the variance in the data. The full model will enable the comparison the accumulation of imaging-based body composition measures vs. BMIz alone and their associations with change in physical activity, sedentary behavior, and cardiometabolic risk factors in children. Finally, there are no standard accepted definitions of pediatric severe obesity to dichotomize participants based on MRI or DXA measures of body fat. Therefore, receiver operating characteristic curves will be created to estimate the value at which visceral, trunk, and body fat best correspond with the BMI definition of severe obesity (i.e. $BMI \ge 120\%$ of the 95th percentile1). Clinically relevant cut-points of severe obesity based on total, trunk, and visceral body fat will be established among this diverse cohort of adolescents.

Power analysis

Objective 1:

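### The fat cut-points are set only by agreement with the BMI class, so calling them clinically relevant is unsupported until they are tested against a health outcome

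*Combined protocol and SAP*

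**What the plan says.** The cut-point step closes the Objective 2 part of Statistical Analysis. Its stated reason is that "there are no standard accepted definitions of pediatric severe obesity to dichotomize participants based on MRI or DXA measures of body fat". The method is to use ROC curves to "estimate the value at which visceral, trunk, and body fat best correspond with the BMI definition of severe obesity". The next sentence gives the product: "Clinically relevant cut-points of severe obesity based on total, trunk, and visceral body fat will be established among this diverse cohort of adolescents". No condition is attached.

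The reference class is anthropometric. Under Description of tests and procedures, BMIz, the text reads "Severe obesity will be categorized as" at or above 120% of the 95th BMI percentile.

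A health outcome is defined elsewhere in the same document. Under Cardiometabolic risk factors: "Elevated cardiometabolic risk (i.e. metabolic syndrome) will be categorized as the presence of three or more cardiometabolic risk factors". The fat measures meet such outcomes in separate models, described under both Objective 1 and Objective 2: "Secondary analysis will use MRI and DXA as covariates in the model (namely the visceral, trunk, and total body fat"). Those models compare the imaging measures with BMIz alone. They do not mention the cut-points.

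**The concern.** The ROC step has two inputs, a fat measure and the BMI class. What it can show is how well a fat value reproduces that class. Whether children above the value have worse health is a separate question, and the step holds no information on it.

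The plan names no criterion for choosing the point on the curve, no minimum discrimination, no validation step and no later test against an outcome. Nothing in it could therefore lead the investigators to withhold the clinical label from any of the three fat measures.

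The protocol's own background makes this matter. In explaining the imaging it says: "Health consequences associated with obesity differ based on where adipose tissue is stored". A reader of the published values would take a clinically relevant visceral-fat threshold to mean one linked to health, when it had been tuned only to match BMI.

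**Working it through.** **1. No figure to reproduce.** The plan gives no AUC, target sensitivity or specificity, selection criterion or sample size for the ROC analysis. The check is mainly a reading of the text, followed by an illustration.

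**2. The relevant places side by side.**

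| Step | Inputs | Health outcome used? | Cut-points used? |
|---|---|---|---|
| ROC step, Objective 2 | Total, trunk, visceral fat; BMI class | No | Produces them |
| Secondary models, Objectives 1 and 2 | Fat measures as covariates; BMIz | Yes (activity, sedentary behavior, cardiometabolic risk factors) | No |
| Main models, Objective 1 | BMIz; severe obesity by BMI | Yes | No |
| High versus low fat gainers, Objective 2 | Percentile split of change in total fat | Yes | No, a different split |

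No row has both an outcome and the cut-points.

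**3. Illustration.** Inputs from the documents: N = 345 (the maximum sample) and about 50% severely obese (Number of Participants). Assumptions: fat-BMI correlation ρ from 0.6 to 0.9, normal variables, and the cut-point chosen by the Youden index J = sensitivity + specificity − 1. Risk is generated in two ways:
- linked to fat, with logit(risk) = −1.2 + 1.0 × fat;
- unlinked, with probability 0.25 for every child.

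Means over 200 runs per correlation:

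| ρ | AUC against BMI class | J | Risk difference, linked | Risk difference, unlinked |
|---|---|---|---|---|
| 0.6 | 0.78 | 0.44 | 0.27 | 0.001 |
| 0.7 | 0.83 | 0.52 | 0.27 | 0.003 |
| 0.8 | 0.88 | 0.61 | 0.27 | 0.001 |
| 0.9 | 0.94 | 0.73 | 0.27 | −0.001 |

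The risk difference is the proportion at risk above the cut-point minus the proportion below it. In each run the cut-point and the AUC against BMI class are the same in both settings, because risk is not an input to either. The unlinked result of zero was built in. The informative part is that the planned output looks identical in the two settings.

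The runs use the maximum N. Allowing for the 12% whom Anticipated Dropout expects to lose to weight limits or refusal of procedures such as the scans gives 345 × 0.88 = 303.6, about 304. Runs at that size gave the same AUCs of 0.83, 0.88 and 0.94 at ρ = 0.7, 0.8 and 0.9.

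**4. Side check on J.** With normal variables and a median split, the best cut-point is the median, where J = (2/π) × arcsin(ρ):
- ρ = 0.6: 0.637 × 0.644 = 0.41
- ρ = 0.7: 0.637 × 0.775 = 0.49
- ρ = 0.8: 0.637 × 0.927 = 0.59
- ρ = 0.9: 0.637 × 1.120 = 0.71

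The simulated values are higher by 0.02 to 0.03, because the cut-point is chosen and assessed on the same children. Any interval should therefore repeat the selection.

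**The case against.** The strongest reply is that the step does what it sets out to do. Severe obesity is defined by BMI throughout the protocol, imaging has no accepted definition, and finding the fat values that match the BMI definition is a sensible translation. That stands: BMI is a proper reference for that purpose, and the ROC analysis should be kept.

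A second reply is that the BMI class already carries risk. The background describes children with severe obesity as the group at highest medical risk, and Objective 1 relates BMIz and severe obesity to cardiometabolic measures in these same children. So indirect evidence will exist. It does not settle the matter, because the plan neither states nor tests that the risk carries over to a fat cut-point. The background also reports more total fat but less visceral adiposity in African American than in White adolescents, so the transfer should not be assumed for each depot.

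A reader might go further and infer that the study throws away what MRI and DXA add. The documents do not support that: the secondary models compare imaging measures with BMIz alone against activity, sedentary behavior and cardiometabolic risk factors. A reader might also take the simulation as a sign that the cut-points will prove unrelated to health. It is not. The unlinked setting is an assumption, and the background reports that trunk fat affects metabolic risk in the earlier WAIST cohort.

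**Conclusion.** The point holds for the cut-points and their label. They are derived from the BMI class alone, they are promised as clinically relevant without condition, and no analysis in the document tests them against a health outcome. This follows from the text and depends on none of the simulation's assumptions (the correlations, the Youden criterion and the two risk models). The simulation shows only that good agreement with BMI class cannot by itself establish relevance to risk. The size of any real gap cannot be estimated from the documents.

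The consequence is limited. This is a supplementary Objective 2 analysis. The primary outcomes are changes in, or relationships with, sedentary behavior, and the sample-size calculations for Objectives 1 and 2 do not rest on the ROC step. It would be wrong to infer that the main hypotheses or the power are affected. What changes is what the study may say about the cut-points, and the improvement is cheap.

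**What to change.** 1. Call the ROC results *fat values equivalent to the BMI definition of severe obesity*, and state the criterion by which each is chosen.
2. Pre-specify an analysis of each cut-point against the elevated cardiometabolic risk outcome already defined under Cardiometabolic risk factors (three or more factors).
3. Add a sensitivity version without waist circumference, which is itself an adiposity measure. The Objective 1 contingencies already allow that no severely obese child may fall below the 90th percentile for waist. State beforehand how many of the remaining factors count as elevated risk.
4. Report sensitivity, specificity and AUC for each cut-point beside those of the BMI class. For a two-category classifier AUC = (sensitivity + specificity)/2, so the two compare directly. Use bootstrap intervals that repeat the cut-point selection in every resample.
5. Describe a cut-point as clinically relevant only if that analysis supports it. The documents offer no basis for a particular bar, so the investigators should set it before the analysis.

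The cost is a change of wording and one further analysis on data already being collected. The downside is that some depots may yield no cut-point that can carry the clinical label.

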We will include adolescents aged 10 to 16 years. We selected this age range because adolescence is a developmental period of rapid fat gain and changes in activity patterns. By choosing the maximum age as 16 years at baseline, the children are likely to still live in Baton Rouge and attend high school at the second clinic visit (age 18 years), facilitating follow-up.

Inclusion Criteria:

- Age 10-16 years
- Body weight < 500 lbs.
- Ability to understand instructions and complete all study procedures

Exclusion Criteria:

- Pregnant
- On a restrictive diet due to illness
- Significant physical or mental disabilities that impede walking, wearing accelerometer or GPS, or responding to EMA.

In addition to the exclusion criteria listed above, participants who refuse to provide written assent, or whose parents or legally authorized representative refuse to sign an informed consent document, will be excluded from the study. Consent/assent will be obtained upon each participant's arrival at the PBRC Pediatric Research Clinic before participating in any study procedures. To further safeguard participant safety and internal validity of the study, inclusion and exclusion criteria will be reassessed by PBRC clinic staff following the completion of required assent/consent forms. The principal investigator and medical investigator have the right to withdraw a participant from the study at any point for any reason.

Number of Participants

We will identify and recruit up to 345 boys and girls aged 10 to 16 years. The sample will be screened on the telephone in attempt to achieve a comparable sex and race distribution. We will oversample for severely obese youth so they comprise approximately 50% of the sample (with the other 50% being distributed among normal weight, overweight, and obese status).

Recruitment Methods

Recruiting children for clinical studies is challenging, particularly those from high risk populations such as with severe obesity and from ethnic minority groups. However, we are confident we can recruit up to 345 children within 2 years. A key recruitment strategy will be to enroll participants who completed the WAIST Study.¹⁶ Of 423 initial participants who were assessed for the WAIST Study in 2010-11, 386 (91.3%) agreed to be re-contacted. Of these, 193 participants will meet the age criteria for the follow-up

Page 7 of 35

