We expect challenges in following up with this cohort 2 years after the Year 0 clinic visit. We will employ several retention strategies between Years 0 and 2 that have been successful in prior trials, including mailing birthday cards to child participants, sending quarterly newsletters on family and children's health topics, inviting families to the annual Pennington Biomedical 5K, and telephoning the parent 2 months prior to the Year 2 clinic visit to schedule the visit and answer questions. The child will receive a stipend after each completed clinic visit and upon returning the accelerometer/GPS tracker, and the child will receive a certificate of completion upon finishing the study. Additionally, Pennington Biomedical has an excellent retention rate for clinical trials. The population of Baton Rouge is relatively stable, 82 and the majority of children will still be enrolled in K-12 school. Offering assessments during summer and school holidays will increase the likelihood of participation. We successfully followed up with children in prior prospective trials: 87% of children aged 10 to 14 years returned for a 2-year followup clinic visit in our Baton Rouge Children's Study (114 of the initial 131).77 Our retention for adult clinical trials is also excellent: we examined 14 trials conducted at Pennington Biomedical with a total of 1581 participants and observed a 70% retention rate over an average 4.8 year follow-up (range 1 year to 13 years). We expect an even higher retention rate due to the shorter follow-up time (2 years). Pennington Biomedical staff may contact participants every 3-6 months by phone or email to maintain contact between Year 0 and Year 2 clinic visits as well as schedule the Year 2 visit.

Anticipated Dropout

The 25% dropout rate is a combined estimate for both loss to follow-up and exclusions that occur during the clinic visit. Based on attrition at 2-year follow-up for Pennington Biomedical's Baton Rouge Children's Study,77 13% of the sample is expected to not report back for the 2-year follow up. An additional 12% is expected to be excluded due to exceeding weight limitations or the refusal of certain procedures (e.g. MRI, DXA) based on refusal rates in Pennington Biomedical's WAIST Study.20

Statistical Analysis

Objective 1:

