The primary outcome for the first objective is change in minutes of sedentary behavior between Year 0 and Year 2 (i.e. Year 2 values minus Year 0 values). Baseline estimates for the two groups were calculated using the WAIST cohort data (from the 2010-11 assessment). Based on data from Berkey et al.,75 the SO group is assumed to increase their sedentary time by 30 minutes/day at year 2, while smaller increases in sedentary time is expected for the NSO group (**Table 5**). A minimum of 334 participants is needed to ensure a well-powered study with significance level of $\alpha = 0.05$, 80% power to detect a 24 minute difference change in sedentary behavior between the two groups, and allowing for a dropout rate of 25%. Therefore, our sample size of up to 345 participants will be sufficient.

Change in minutes/day of sedentary time for NSO group	Change in minutes/day of sedentary time for SO group	Difference in change between groups	Standard deviation of change between groups	Minimum sample size	Total sample size (allows for 25% dropout)
2.4	30.0	27.6	69.6	202	253
3.6	30.0	26.4	69.6	222	278
4.8	30.0	25.2	69.6	242	303
6.0	30.0	24.0	69.6	266	334

Table 5. Difference in changes in sedentary time based on severe obesity status. *Note.* NSO is the group classified as not severely obese; SO is the group classified as severely obese.

Note. NSO is the group classified as not severely obese; SO is the group classified as severely obese.

Secondary analyses will include change in daily MVPA minutes between years and change in days/week of physical activity (\geq 60 minutes MVPA/day) between years. Power analysis was conducted on these outcomes, using the WAIST cohort and data from Nigg et al.,76 and our sample size will have power of 93.8% and 90.4% to detect a significant difference in change in daily MVPA minutes and change in days/week of physical activity, respectively.

Contingencies

Based on national reference data, it is possible that very few or no severely obese children meet the healthy behavior or cardiometabolic health criteria (e.g. no severely obese child attains ≥ 60 minutes of MVPA/day; no severely obese child has a waist circumference < 90th percentile). If this is the case, the dichotomous dependent variable will be adjusted to be quartiles, so that the analyses is interpreted as the likelihood of a severely obese child being in the top (healthiest) quartile of the health behavior or cardiometabolic health criteria for the overall cohort.

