Objective 2:

The primary outcome for the second objective is the relationship between total fat accumulation and change in sedentary behavior. Based on data from Berkey et al.,75 we estimate an overall change in sedentary behavior of 12 minutes/day increase in the HFG and 3.6 minutes/day increase in the LFG over a two-year period. **Table 6** shows sample sizes required to detect various differences for the change between groups. With a sample size of up to 345, this will provide at least 80% power for detecting a difference in the change between groups of 8.4 minutes/day, allowing for the anticipated 25% dropout. Therefore, with our sample size of up to 345 participants, we will have sufficient power to detect a difference between the HFG and LFG groups.

Change in minutes	Change in minutes	Change between	Standard deviation	Minimum sample	Total sample size
of sedentary time	of sedentary time	groups	of change between	size	(allows for 25%
for HFG	for LFG		groups		dropout)
12	2.4	9.6	24	194	259
12	3	9.0	24	220	293
12	3.6	8.4	24	255	Up to 345
12	4.2	7.8	24	292	389

Table 6. Difference in changes in sedentary time between the high fat vs. low fat gainer group. *Note.* HFG is the group classified as high fat gainers; LFG is the group classified as low fat gainers.

Secondary analyses based on the second objective will include modeling the relationship between fat mass accumulation and change in physical activity. Using data from Berkey et al.,75 we estimate an overall decrease of 19.2 minutes/day of MVPA in the HFG and a decrease of 4.8 minutes/day of MVPA in the LFG over a two-year period. With a sample size of up to 345 (including anticipated dropout), this will provide 93.4% power for detecting a difference in the change between groups of 14.4 minutes/day.

Contingencies

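### Table 5 allows for 25% dropout by multiplying by 1.25 rather than dividing by 0.75; on the plan's own inputs Objective 1 needs 355 participants, above both the stated minimum of 334 and the ceiling of 345

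*Combined protocol and SAP*

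**What the plan says.** The Objective 1 part of the Power analysis section takes change in sedentary time from Year 0 to Year 2 as the primary outcome, comparing severely obese (SO) with not severely obese (NSO) participants. It states "A minimum of 334 participants is needed to ensure a well-powered study" and specifies "80% power to detect a 24 minute difference change in sedentary behavior between the two groups", a significance level of 0.05 and a 25% dropout allowance. It then concludes: "Therefore, our sample size of up to 345 participants will be sufficient".

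These figures come from the last row of Table 5: NSO change 6.0, SO change 30.0, difference 24.0, SD 69.6, minimum 266, total 334.

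The Anticipated Dropout section defines the allowance: "The 25% dropout rate is a combined estimate for both loss to follow-up and exclusions that occur during the clinic visit". It is made up of 13% of the sample not returning at two years and a further 12% excluded for weight limits or refused procedures.

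For Objective 2, Table 6 applies the same 25% allowance, and the text says: "With a sample size of up to 345, this will provide at least 80% power".

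**The concern.** If 25% of those enrolled are lost, 75% remain, so the enrolment target is the evaluable number divided by 0.75. Table 5 instead adds 25% to the evaluable number, which covers a loss of only about 20%. Table 6, under a near-identical column heading, divides by 0.75 in three of its four rows. One plan therefore uses two dropout rules.

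At stake is the stated power for the primary outcome of the first objective. The figure of 334 is offered as the reason that 345 suffices. If 334 is too low, that reasoning fails, and the correct figure may exceed the enrolment ceiling. The Stopping rules paragraph also provides for a yearly review of whether recruitment or attrition jeopardises the aims; a review that used 334 as its benchmark would understate the enrolment needed.

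**Working it through.** **Inputs.** From Power analysis, Objective 1 and Table 5: differences of 27.6, 26.4, 25.2 and 24.0 min/day, SD of change 69.6, alpha 0.05, power 80%, dropout 25%. From Number of Participants: "We will oversample for severely obese youth so they comprise approximately 50% of the sample", hence about 1:1 groups. The plan does not say whether the test is one- or two-sided. Two-sided reproduces the table; one-sided would give 208 rather than 266 in the last row.

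**Step 1: reproduce the evaluable numbers.** The normal approximation for the total is n = 4(1.96 + 0.8416)² × (69.6/24)² = 4 × 7.849 × 8.41 ≈ 264.0. That is 132.02 per group, rounded up to 133, so 266 in total. The two-sample t-test version gives 265.97, again 266. Rounded up to equal groups, the t-test version matches all four printed minimums (202, 222, 242, 266). This column is right.

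**Step 2: identify the inflation rule.**

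| Difference (min/day) | Minimum n | n × 1.25 | n / 0.75 | Printed total |
|---|---|---|---|---|
| 27.6 | 202 | 252.5 | 269.3 → 270 | 253 |
| 26.4 | 222 | 277.5 | 296.0 → 296 | 278 |
| 25.2 | 242 | 302.5 | 322.7 → 323 | 303 |
| 24.0 | 266 | 332.5 | 354.7 → 355 | 334 |

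The first three totals are n × 1.25 rounded up. The last is one above the rounded product of 333. None follows n/0.75.

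**Step 3: compare with Table 6.** 194/0.75 = 258.7 (printed 259), 220/0.75 = 293.3 (printed 293) and 292/0.75 = 389.3 (printed 389). The design row, 255/0.75 = 340, is printed as up to 345. It matches neither rule exactly but is closer to division than to 255 × 1.25 = 318.75.

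**Step 4: power for 24 min/day after 25% loss** (two-sided t-test, SD 69.6, equal groups).

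| Enrolled | Evaluable (× 0.75) | Power |
|---|---|---|
| 334 | 250.5 | 77.5–77.6% |
| 340 (final goal in Table 7) | 255 | 78.3% |
| 345 | 258.75 | 78.8–78.9% |
| 355 | 266.25 | 80.0% |

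Where a range is shown, the lower value rounds the evaluable number down (250, 258).

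**Step 5: the same shortfall in other terms.** Loss tolerated before falling below 266 is 1 − 266/334 = 20.4% at 334 and 1 − 266/345 = 22.9% at 345. With 25% loss, the difference detectable at 80% power is about 24.7 min/day at 334 and 24.3 to 24.4 min/day at 345.

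**Step 6: sensitivity to the attrition rate.** If only the 13% non-return applied, 266/0.87 = 305.7, so 306 would be needed. Then 345 × 0.87 ≈ 300 evaluable gives 84.5% power, and 334 × 0.87 ≈ 291 gives about 83%.

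**The case against.** The arithmetic is hard to dispute; the case on the other side is about weight.

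- **The shortfall is small.** At 345 with the full 25% loss, power is about 1 point under target. The other three scenarios in Table 5 keep more than 80% (82.7%, 86.0% and 88.8% for 25.2, 26.4 and 27.6 min/day), and their corrected totals all lie below 345. This stands. However, 24 min/day is the difference the text names as its target, and it is the row from which 334 is taken.
- **The 25% may be too high for this outcome.** The 12% component concerns weight limits and refused procedures, with MRI and DXA as the examples. The Objective 1 exposure is based on BMI, the outcome is accelerometer sedentary time, and scan measures enter only secondary models. The Objective 2 contingency keeps children who exceed scanner limits and classifies them by anthropometry. On a 13% loss, 345 is ample. This is a reasonable argument, but the plan does not make it: the Objective 1 text applies 25%, and the Anticipated Dropout section describes the 12% as excluded. It would be a different justification and would not make the printed column correct.
- **Table 6 is an imperfect benchmark.** Its design row does not follow the division rule exactly, and its minimums (194, 220, 255, 292) are slightly below what the t-test gives (about 198, 225, 258, 299). That is fair. The case for dividing by 0.75 rests on the plan's definition of dropout as a share of the sample; Table 6 only shows that the plan is inconsistent.
- **No enrolment decision turns on it.** The protocol version is dated 3/1/2021 and recruitment was expected to end in spring 2018. That is a reason to ask for a corrected statement, not more participants.

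**Conclusion.** The point holds: the statement is wrong as written. Under the plan's own 25% loss, 80% power for 24 min/day needs 355 enrolled (356 for exactly equal groups). That is 21 more than the stated minimum and 10 more than the ceiling. The Table 5 totals are about 6% low throughout. Power is about 77.5% at 334 and about 79% at 345, against the 80% claimed.

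This rests on a two-sided two-sample t-test, SD 69.6, roughly equal groups and 25% of enrolled participants being lost. The figure of 355 depends on that loss rate; at 13% the conclusion that 345 suffices would be correct, but the documents do not use 13% for this objective. The practical effect is slight: no analysis changes and only the most demanding row of Table 5 misses its target. It is still worth correcting, because it is the stated sample size justification for a primary outcome.

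**What to change.** Recompute the last column of Table 5 as n/(1 − 0.25): 270, 296, 323 and 355. Replace the two sentences on sufficiency with a statement that 355 would be needed for 80% power at 24 min/day, and that up to 345 enrolled with 25% loss gives about 79% power, or 80% power for a difference of about 24.3 to 24.4 min/day.

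Alternatively, state and justify a separate attrition rate for the accelerometer outcome and rebuild the column from it. With 13% loss, the 24 min/day row becomes 306 and power at 345 is 84.5%. Either way, use one dropout rule in both tables, reconcile the design row of Table 6 (255/0.75 = 340, printed as up to 345), and state that the test is two-sided.

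The cost is one table column and a few sentences. With 25% loss retained, the stated power becomes slightly less favourable. No extra enrolment is needed.
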